8.2.5 Statistical Methods

Statistical testing and inference for efficacy and safety analyses are described in Sections 8.2.5.1 and 8.2.5.2. Controlling of family-wise Type I error rate is described in Section 8.2.6, Multiplicity. Nominal p-values will be computed for tertiary and exploratory efficacy analyses as a measure of strength of association between the endpoint and the treatment effect rather than formal tests of hypotheses. Unless otherwise stated, all statistical tests will be conducted at $\alpha=0.05$ (2-sided) level.

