8.2.7 Sample Size and Power Calculations

A total of approximately 1000 subjects will be randomized in a 1:1 ratio to either MK-3641 or placebo. Assuming a 15% dropout rate, this gives approximately 425 evaluable subjects per treatment group.

With 425 subjects per arm, the study will have:

- approximately 90% power (2-sided, $\alpha = 0.05$) to have the upper bound of the 95% CI for relative difference below -10%, and
- more than 90% power (2-sided, $\alpha = 0.05$) to have an estimated relative difference below -15%.

The calculations are based on the assumptions that the true difference between treatment arms in average TCS during peak RS is -2.12, that the average TCS during peak RS from the placebo group is 8.9, and that the standard deviation is 5.60. These assumptions, as well as the assumption on dropout rate, are based on the two MK-3641 (AIT ragweed) adult studies, P05233 and P05234, and the pediatric trial P05239 for MK-7243 (AIT grass).

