##### 3.1.1 Efficacy Analyses

##### Primary Efficacy Analysis

The primary analysis will be conducted on the Full Analysis Set (FAS) population. The FAS population includes all subjects who receive at least one dose of study treatment. Subjects will be analyzed according to the treatment group to which they are randomized.

The primary efficacy endpoint for the current trial is the average TCS during the peak ragweed season. It will be analyzed using the analysis of variance (ANOVA) model, which includes fixed effects of treatment, baseline asthma status (yes, no), age group (5 to 11 years, 12 to 17 years), pollen season, and pollen region nested within pollen season. Pollen region will be defined based on pollen station and may include several sites within an acceptable distance between the pollen counters and corresponding sites. To avoid failure in model convergence, observed in model testing on the blinded data, pollen region will be defined by participating countries, except for the United States, which will be split into 2 pollen regions.

Two-sided 95% confidence interval (CI) of the treatment difference in adjusted means will be presented. Also, the treatment difference in adjusted means relative to the adjusted mean of the placebo group will be presented as a percentage with corresponding 2-sided 95% CI derived using the bootstrap method. No missing data will be imputed.

The normality assumption of the ANOVA model will be checked using the Shapiro-Wilk test and inspection of the Q-Q plot. If a severe violation is observed, the primary analysis will be based on Wilcoxon Rank Sum test; the p-value will be reported together with the associated Hodges-Lehmann estimate of the treatment difference and its 2-sided 95% CI. Also, the difference in the treatment group medians relative to the median of the placebo group will be presented as a percentage with the corresponding 2-sided 95% CI derived using the bootstrap method.

A Per Protocol (PP) analysis will be conducted for the primary efficacy endpoint, where the same ANOVA model and missing data approach will be used. See Section 3.2.5.1 for further sensitivity analyses of the primary efficacy endpoint.

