##### **3.2.5.1 Statistical Methods for Efficacy/Immunologic Analyses**

###### **Primary Efficacy Analysis**

The primary efficacy endpoint for the current trial is the average TCS during the peak ragweed season. It will be analyzed using the ANOVA model, which includes fixed effects of treatment, baseline asthma status (yes, no), age group (5 to 11 years, 12 to 17 years), pollen season, and pollen region nested within pollen season. Pollen region will be defined based on pollen station and may include several sites within an acceptable distance between the pollen counters and corresponding sites.

Two-sided 95% CI of the treatment difference in adjusted means will be presented. Also, the treatment difference in adjusted means relative to the adjusted mean of the placebo group will be presented as a percentage with corresponding 2-sided 95% CI derived using the bootstrap method. No missing data will be imputed.

The normality assumption of the ANOVA model will be checked using the Shapiro-Wilk test and inspection of the Q-Q plot. If a severe violation is observed, the primary analysis will be based on Wilcoxon Rank Sum test; the p-value will be reported together with the associated Hodges-Lehmann estimate of the treatment difference and its 2-sided 95% CI. Also, the difference in the treatment group medians relative to the median of the placebo group will be presented as a percentage with the corresponding 2-sided 95% CI derived using the bootstrap method.

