### 3.2.8 Sample Size and Power Calculations

A total of approximately 1000 subjects will be randomized in a 1:1 ratio to either MK - 3641 or placebo. Assuming a 15% dropout rate, this gives approximately 425 evaluable subjects per treatment group.

With 425 subjects per arm, the study will have:

- approximately 90% power (2-sided,  $\alpha = 0.05$ ) to have the upper bound of the 95% CI for relative difference below -10%, and
- more than 90% power (2-sided,  $\alpha = 0.05$ ) to have an estimated relative difference below -15%.

The calculations are based on the assumptions that the true difference between treatment arms in average TCS during peak RS is -2.12, that the average TCS during peak RS from the placebo group is 8.9, and that the standard deviation is 5.60. These assumptions, as well as the assumption on dropout rate, are based on the two MK-3641 (AIT ragweed) adult studies, P05233 and P05234, and the pediatric trial P05239 for MK-7243 (AIT grass).

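### An undefined 'severe violation' of normality, with no step before unblinding, can replace the adjusted ANOVA by an unstratified Wilcoxon test and relative medians, and the strategy tables give a different trigger

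*SAP*

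**What the plan says.** Protocol 8.1.1 and 8.2.5.1 and sSAP 3.1.1 and 3.2.5.1 carry the same rule. The primary comparison is an ANOVA with terms for treatment, baseline asthma, age group, pollen season and pollen region within season. The headline percentage is the difference in adjusted means over the adjusted placebo mean, with a bootstrap interval. Normality is then checked by Shapiro-Wilk and a Q-Q plot, and "If a severe violation is observed, the primary analysis will be based on Wilcoxon Rank Sum test". A Hodges-Lehmann estimate with its interval accompanies that test, and "the difference in the treatment group medians relative to the median of the placebo group will be presented as a percentage". No strata or covariates are named for the Wilcoxon test.

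A different condition appears in the strategy tables (Protocol Tables 8 and 10; sSAP Tables 1 and 3). There the Wilcoxon row carries footnote c, which applies the method when the data contain too many zeros. The same footnote marks the zero-inflated model for the medication score.

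The sample size text (Protocol 8.2.7, sSAP 3.2.8) states about 90% power "to have the upper bound of the 95% CI for relative difference below -10" per cent. It assumes that "the true difference between treatment arms in average TCS during peak RS is -2.12", with a placebo mean of 8.9 and an SD of 5.60.

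**The concern.** Three things are left open for the test that decides the trial.

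- **Threshold.** No p-value, W statistic, skewness or Q-Q limit defines *severe*. The plan's other data-driven triggers are numeric: more than 30% zero daily medication scores, and more than 2% of subjects on prednisone.
- **Timing and assessor.** Nobody is named to decide. Residuals from a model with a treatment term need the treatment codes. Protocol 8.2.1 and sSAP 3.2.1 list what must be finished before unblinding, and this decision is not listed.
- **Which trigger governs.** The text says non-normality; the footnote says excess zeros. Protocol 8.2.5.1 and sSAP 3.2.5.1 also warn, for the medication score, that many zeros may stop a non-parametric method from working properly. That sits badly with a footnote that sends the primary endpoint to Wilcoxon for the same reason.

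A switch changes more than the test. Covariate adjustment is lost, although randomization is stratified by age and asthma. The effect moves from means to medians, beside a Hodges-Lehmann shift that is not a difference in medians. The per-protocol, LOCF, multiple-imputation and same-day-entry analyses and the subgroups stay on the ANOVA, so they would no longer examine the reported primary result.

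**Working it through.** **Inputs.** From Protocol 8.2.7 and sSAP 3.2.8: "Assuming a 15% dropout rate, this gives approximately 425 evaluable subjects per treatment group" (1000 × 0.85 / 2 = 425); placebo mean 8.9; difference -2.12, so active mean 8.9 - 2.12 = 6.78 and relative difference -2.12/8.9 = -23.8%; SD 5.60. From Protocol 8.2.5: two-sided α = 0.05. From Protocol 4.2.3.1.1: symptom score 0-18 plus medication score 0-20, so TCS runs from 0 to 38.

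**1. The plan's power.** SE = 5.60 × √(2/425) = 0.384. With the placebo mean treated as fixed, -10% is -0.89:
- upper bound below -10%: Φ((2.12 - 0.89)/0.384 - 1.96) = Φ(1.24) = 89.3%, against a stated figure of about 90%;
- estimate below -15% (-1.335): Φ((2.12 - 1.335)/0.384) = Φ(2.04) = 97.9%, against more than 90%;
- plain superiority: Φ(2.12/0.384 - 1.96) = Φ(3.56) = 99.98%.

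The stated figures are reproduced, and they rest on means only.

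**2. Normality at the planning values.** A normal distribution would put Φ(-8.9/5.60) = 5.6% of placebo and Φ(-6.78/5.60) = 11.3% of active subjects below zero, which the scale does not allow.

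**3. What Shapiro-Wilk would say with 850 residuals (simulated).** The shape is not in the documents, so several were tried.

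| Shape | Rejects at 0.05 | Rejects at 0.001 | Mean W | Skewness |
|---|---|---|---|---|
| Gamma, lognormal, beta, Weibull, truncated normal, floored normal matched to the mean and SD | 100% | 100% | 0.81 to 0.97 | 0.5 to 2.4 |
| Normal simply floored at zero, region cells explaining 0% to 40% of variance (assumed) | 100% falling to 81% | 100% falling to 31% | 0.984 to 0.994 | 0.3 to 0.2 |

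Formal rejection is close to certain for most shapes, so it separates little. In the mildest case W is so near 1 that a reader of the Q-Q plot might well not call the departure severe.

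**4. Test power.** For the shapes in the first row, the t-test and the Wilcoxon test each had power of about 99.9% or more.

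**5. Effect measure, gamma data.** The gamma shape parameter is (mean/SD)². Placebo: (8.9/5.60)² = 2.53, median 7.76.
- Active with equal SD 5.60: (6.78/5.60)² = 1.47, median 5.32; relative median 5.32/7.76 - 1 = -31%.
- Active with equal coefficient of variation: SD 5.60 × 6.78/8.9 = 4.27, median 5.91; relative median 5.91/7.76 - 1 = -24%.

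Simulated chance that the bootstrap upper bound lies below -10% (425 per arm, 400 trials, 400 resamples, no covariates):

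| Gamma scenario | Means | Medians |
|---|---|---|
| Equal SD 5.60 | 91% | 98% |
| Equal coefficient of variation | 97% | 81% |

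Simulation error is at most about √(0.81 × 0.19/400) = 2 points. In the second scenario the median-based interval is 34% wider (0.171 against 0.128). A large-sample approximation over other shapes gives 83% to 95% on medians when the drug scales the whole distribution. With equal SDs it gives 93% to more than 99%, with relative medians of -29% to -35%.

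**6. Type I error (gamma null, 4000 runs, no covariates).** t-test 0.045; Wilcoxon 0.048; mechanical rule at Shapiro-Wilk p < 0.05, 0.048; free choice of the smaller p-value, 0.0635.

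**The case against.** The strongest defence is that the fallback is pre-specified, in the same words in four places, with its test, estimator and interval. That stands: the rule exists in advance, and what is open is its application.

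A reader might infer several stronger things that the documents do not support.

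- *The switch is almost certain.* The trigger is a judged severe violation from a test and a plot together, not p < 0.05. Near-certainty is shown for the Shapiro-Wilk rejection only.
- *The trial's success criterion would change.* The -10% and -15% figures stand only in the power text. The hypothesis is a significant reduction, and the fixed sequence asks only for statistical significance.
- *Power would fall.* Superiority power is unaffected. For the -10% bound, step 5 shows a fall in one scenario and a rise in the other. The equal-SD case, where it rises, is closer to the plan's single SD of 5.60.
- *Type I error is inflated.* Just over 6% needs a free choice of the better p-value, which the plan does not grant.
- *Mixing test types breaks the fixed sequence.* It does not. Sequential control needs no common test, and the plan already allows a zero-inflated model for the medication score.

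A numeric trigger applied to blinded pooled data, with a stratified rank test, would also close the gap. It would still leave the sizing and the sensitivity analyses on a different measure from the primary result.

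**Conclusion.** The point holds as a defect of specification. An undefined threshold, possibly applied after unblinding and contradicted by footnote c, selects the primary test and the headline percentage. The Shapiro-Wilk half of the check is nearly uninformative at this sample size, so the decision falls to the eye, and no probability of a switch can be given.

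The cost is mainly in interpretation. The reported percentage can move by about 7 points (-24% to -31%) with no change in the drug's effect, or stay the same with a clearly wider interval. The stated power of about 90% applies only to the mean-based measure. Against this the fallback offers no needed gain, since with 425 per arm a comparison of means does not depend on normal data.

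These sizes rest on assumptions outside the documents: the distribution shape, the share of variance due to region, and SD 5.60 read as the SD in each arm (the plan does not say whether it is total or residual). The gap in threshold and timing and the conflict with footnote c need none of them.

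**What to change.** By protocol amendment and sSAP update before unblinding:

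1. In Protocol 8.1.1 and 8.2.5.1 and sSAP 3.1.1 and 3.2.5.1, state that the adjusted ANOVA, with the bootstrap interval already planned for the relative difference in adjusted means, is the primary analysis whatever the normality check shows.
2. Report Wilcoxon and Hodges-Lehmann as a named sensitivity analysis.
3. Drop the median-based percentage as a replacement for the primary effect measure.
4. Remove footnote c from the Wilcoxon row in Protocol Tables 8 and 10 and sSAP Tables 1 and 3, and keep it on the zero-inflated row.

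The cost is wording. No new data are needed, and the rank-based result is still reported. An amendment is the route that Protocol 8.2 and sSAP 3.2 themselves require for a change to primary methods. Settling model questions while blinded is also practicable here: sSAP 3.1.1 redefines pollen region "To avoid failure in model convergence, observed in model testing on the blinded data". The downside is that if the data prove very skewed, the rank-based result is supportive only.

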### Sensitivity Analysis

The PP analysis will be conducted for the primary efficacy endpoint, where the same ANOVA model and missing data approach will be used. In addition, the following sensitivity analyses will be performed for the primary efficacy endpoint.

- The same ANOVA model based on the FAS population will be used. Missing data will be imputed by the LOCF approach. For each subject, only the observations within the pollen season are eligible to be carried forward.
- The same ANOVA model based on the FAS population will be used. Missing data will be handled by the multiple imputation method. Missing data from both treatment groups will be imputed using the sample distribution of TCS observed from the placebo group, which is considered to be a conservative approach for imputations.
- Longitudinal Data Analysis model based on the FAS population will be used. Daily TCS during the peak season will be the response variable and covariates will include treatment, time, the interaction of treatment by time, baseline asthma status, age group, pollen season, and pollen region nested within pollen season. The Toeplitz structure will be used to model the covariance of the repeated TCS measurements over time within subjects. Additional covariance structures, such as unstructured covariance, may be considered if convergence issues are encountered with the analysis model.

Furthermore, if there are more than 2% of subjects taking prednisone during any one ragweed season in the course of the study, a sensitivity analysis will be conducted for the primary efficacy endpoint, where the usage of prednisone is included in the definition of the rhinoconjunctivitis DMS. The medication scores for prednisone usage are defined in [Table 2].

Table 2 Medication Score for Prednisone Usage

Rescue Medication	Subject Dosing Instructions	Score/Dose Unit	Maximum Daily Score
Prednisone tablet 5 mg	Day 1: 1 mg/kg/day, Max 50 mg/day	1.6 (per tablet)	16
	Day 2+: 0.5 mg/kg/day, Max 25 mg/day	1.6 x 2 (per tablet)	16

In addition, in order to minimize missing data, subjects will be allowed to complete the daily e-diary up to 9 am the following morning (in case the subject cannot complete it at their regular time that day). A sensitivity analysis will be conducted for the FAS population, where only the data entered on the same day (instead of next morning) are included. The same ANOVA model and missing data approach will be used.

Moreover, the primary analysis will only consider the rescue medications provided by the study (i.e., reported in the e-diary). Some subjects may take rescue medications that are not provided by the study. A sensitivity analysis will be conducted for the DMS by including these rescue medications if a medication score was pre-specified in the protocol.

### **Key Secondary Efficacy Analyses**

The key secondary efficacy endpoints for the current trial include:

- Average TCS during the entire RS;
- Average rhinoconjunctivitis DSS during the peak RS;
- Average rhinoconjunctivitis DMS during the peak RS.

These endpoints will be analyzed based on the FAS population using the same ANOVA model as the primary efficacy endpoint.

Based on the rescue medication usage from previous AIT trials, many subjects used little rescue medication during the trial, which resulted in large amounts of rhinoconjunctivitis DMS records equal to zero. Data with excessive zeroes may not conform to the normality assumption for the ANOVA model and may also prevent the proper application of non-parametric method. In a situation when there are more than 30% of the daily rhinoconjunctivitis DMS equal to zero, the zero-inflated lognormal model [16] will be used as the primary analysis method for rhinoconjunctivitis DMS as appropriate; this model takes the average rhinoconjunctivitis DMS during the peak RS as response and adjusts for the same terms as in the ANOVA model.

### **Tertiary Efficacy/Immunologic Analyses**

The tertiary efficacy/immunologic endpoints for the current trial include:

- Average rhinoconjunctivitis DSS during the entire RS;
- Change from baseline in IgE level against *Ambrosia artemisiifolia* at Visit 6;
- Change from baseline in IgE level against *Ambrosia artemisiifolia* at Visit 8;
- Change from baseline in IgG4 level against *Ambrosia artemisiifolia* at Visit 6;
- Change from baseline in IgG4 level against *Ambrosia artemisiifolia* at Visit 8.

Average rhinoconjunctivitis DSS during the entire RS will be analyzed based on the FAS population using the same ANOVA model as the primary efficacy endpoint.

IgE and IgG4 related endpoints will be analyzed separately using the constrained LDA (cLDA) model. The cLDA model assumes a common mean across treatment groups at baseline and different means for different treatments at each post-baseline time point. In this model, the response vector consists of the baseline value and the values observed at each post-baseline time point. The model will adjust for time, the interaction of treatment by time, baseline asthma status, age group, pollen season, and pollen region nested within pollen season. Time is treated as a categorical variable so that no restriction is imposed on the trajectory of the means over time. A Toeplitz covariance matrix will be used to model the correlation among repeated measurements. Further details of the model specification, assumptions, and SAS implementation codes are provided in the Appendix.

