2.0 TRIAL DESIGN

2.1 Trial Design

This is a randomized, placebo-controlled, parallel-group, multi-site, double-blind trial of MK-3641 in children with ragweed pollen-induced allergic rhinitis/rhinoconjunctivitis, with or without asthma, to be conducted in conformance with Good Clinical Practices. Approximately 1000 children ages 5 to 17 years will be randomized in a 1:1 ratio to receive either MK-3641, at a dose of 12 Amb a 1-U, or placebo once daily for a total of approximately 20 to 28 weeks. Subjects will be stratified by age to ensure an adequate number of subjects at younger ages are included. Subjects will also be stratified by asthma status. There may be multiple separate cohorts (approximately 2 to 3) recruited over consecutive ragweed seasons to complete the enrollment goal.

The trial consists of a screening period and a treatment period, which includes pre-seasonal and co-seasonal treatment. The screening period may last for up to approximately 12 months prior to randomization. Once randomized, subjects are treated with a minimum of approximately 12 weeks (up to approximately 20 weeks) of pre-seasonal treatment and approximately 8 weeks of co-seasonal treatment. There will be at least 7 clinic visits:

screening (Visit 1), randomization (Visit 2), Off-season (Visit 3), Off-season (Visit 4), Pre-season (Visit 6), In-season (Visit 7), and End-of-season (Visit 8 or Discontinuation Visit); Off-season (Visit 5) is only required if the time between Visit 4 and 6 is longer than 6-8 weeks. Subject compliance with study drug administration, rescue medication use, and daily e-diary completion will be monitored. Compliance issues will prompt site retraining of subject/parent/guardian via telephone contacts as necessary. The End-of-season visit will be scheduled approximately 1 week after the end of the ragweed season. A final telephone contact will occur approximately 14 days after the End-of-season (or discontinuation) visit for the safety follow-up. Unscheduled visits are also permitted, if needed. The trial diagram is outlined in Section 2.2.

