- ^{k.} Vital Signs (axillary temperature, blood pressure, pulse, respiration rate) in a seated position, height, and weight should be performed prior to performing pulmonary function tests. At the End-of-season/Discontinuation visit a limited physical exam will be performed.
- ^{l.} Oropharyngeal examinations will be performed before and after study drug administration at Visit 2. Targeted physical examinations may be conducted at visits that do not already include a physical exam, if deemed necessary by the investigator, due to signs/symptoms.
- ^{m.} FEV₁ results should be available and reviewed by investigator or designee prior to administration of first dose of study medication to ensure results meet inclusion criteria. Following randomization, PFTs are required only for subjects with asthma at the subsequent visits identified in the trial flow chart, unless the investigator feels a PFT is warranted for a subject without asthma. Note: PFTs are not required for those subjects ≤7 years of age who cannot perform reproducible FEV₁ maneuvers despite coaching; those subjects ≤7 years of age who can perform reproducible FEV₁ maneuvers, including those who initially could not at the Screening Visit, must complete the PFTs.
- ^{n.} Beta₂-agonist reversibility (Section 12.9) will be performed at Visit 2 for all subjects performing PFTs (i.e., all subjects >7 years of age and all subjects ≤7 years of age who can perform reproducible FEV₁ maneuvers).
- ^{o.} If a urine test result is positive, confirm with a serum β-hCG test.
- ^{p.} Immunologic samples will only be collected at selected sites. The Visit 2 sample should be collected prior to administration of the first dose of study drug. Leftover main study serum samples will be stored for future biomedical research if the subject consents to future biomedical research.
- ^{q.} Saliva (DNA) for FBR should be the last procedure performed at Visit 2. If not obtained at Visit 2, can be obtained at a subsequent visit once the informed consent for FBR is obtained.

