#### **Tertiary Efficacy/Immunologic Endpoints**

- Average rhinoconjunctivitis DSS during the entire RS
- Change from baseline in IgE level against *Ambrosia artemisiifolia* at Visit 6 and at Visit 8;
- Change from baseline in IgG4 level against *Ambrosia artemisiifolia* at Visit 6 and at Visit 8.

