## APPENDIX: Technical Details for supplemental SAP

### APPENDIX A

#### CONSTRAINED LONGITUDINAL DATA ANALYSIS (CLDA) METHOD (WITH ADJUSTMENT FOR BASELINE VALUES) – TECHNICAL DETAILS FOR MODEL SPECIFICATION, ASSUMPTIONS, AND SAS IMPLEMENTATION CODES

##### Model

Let  $Y_{ijt}$  be the response for subject  $i$ , with treatment assignment  $j$ , at time  $t$ . The marginal mean responses of the cLDA model can be formulated as

$$E(Y_{ij0}) = y_0, \quad j = 0, 1.$$

and

$$E(Y_{ijt}) = y_0 + y_{jt}, \quad j = 0, 1; t = 1, 2, 3, 4.$$

The mean response  $\gamma_0$  at  $t = 0$  is constrained to be the same for all treatment groups due to randomization. The effect  $\gamma_{jt}$  denotes the change from baseline for treatment  $j$  at time  $t$ . The cLDA model assumes that baseline and post-baseline values have a joint multivariate normal distribution. A Toeplitz covariance matrix can be specified in the mixed model to account for within subject correlation at times  $t \geq 0$  (including baseline).

At each time point  $t$ ,  $t = 1, 2, 3, 4$ , the mean change from baseline (LSMEANS) for  $j^{\text{th}}$  dose of test drug and control are  $\gamma_{jt}$  and  $\gamma_{0t}$ , respectively, as defined in the cLDA model above.

The treatment difference for  $j^{\text{th}}$  treatment group vs. control for the mean change from baseline at time point  $t$ ,  $t = 1, 2, 3, 4$  is defined as:

$$\eta_{jt} = Y_{jt} - Y_{0t}.$$

This longitudinal model provides valid statistical inference in the presence of possible missing data if the missing data mechanism is ignorable (or more specifically, missing at random [MAR] or missing completely at random [MCAR]). This missing data mechanism requires that the probability of a data point being missing does not depend on the missing data after adjusting for the observed data.

Reasons for discontinuation from the trial may include lack of efficacy, clinical or laboratory adverse experiences, relocation, withdrawal of consent, protocol violations, and/or data processing issues. Missing data caused by relocation and data processing issues, are likely to be MCAR. On the other hand, missing data caused by discontinuation due to lack of efficacy may belong to MAR because the discontinuation may depend on the observed efficacy outcomes. The

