### **Example SAS Codes**

```
*****.  
** data step necessary prior to running SAS PROC MIXED;  
*****; DATA long; SET long;  
ARRAY T{5} t0-t4; * time indicator variables; ARRAY TT1{5} tt10-tt14;  
  
** define week times treatment 1 indicator variables; DO i = 1 TO 5;  
t{i} = (time=(i-1));  
tt1{i} = t{i}*(trt=1);  
tt2{i} = t{i}*(trt=2);  
END; DROP i; RUN;
```

```
*****.  
** fitting the cLDA model using SAS PROC MIXED;  
*****; PROC MIXED DATA=long;  
  
CLASS subj time stratum; ** subj is the subject id number **; MODEL y=time tt11 tt12 tt13 tt14 tt21 tt22 tt23 tt24 stratum;  
REPEATED time / SUBJECT=subj TYPE=TOEP;  
  
ESTIMATE 'T1 Diff (MK - Placebo)' tt11 1; ESTIMATE 'T2 Diff (MK - Placebo)' tt12 1; ESTIMATE 'T3 Diff (MK - Placebo)' tt13 1;  
ESTIMATE 'T4 Diff (MK - Placebo)' tt14 1;  
  
ESTIMATE 'T1 Placebo LSM' time -1 1 0 0 0;  
ESTIMATE 'T2 Placebo LSM' time -1 0 1 0 0;  
ESTIMATE 'T3 Placebo LSM' time -1 0 0 1 0;  
  
ESTIMATE 'T4 Placebo LSM' time -1 0 0 0 1;  
  
ESTIMATE 'T1 MK LSM' time -1 1 0 0 0 tt11 1;  
ESTIMATE 'T2 MK LSM' time -1 0 1 0 0 tt12 1;  
ESTIMATE 'T3 MK LSM' time -1 0 0 1 0 tt13 1;  
ESTIMATE 'T4 MK LSM' time -1 0 0 0 1 tt14 1;  
  
ODS OUTPUT Estimates=outm1; RUN;
```

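### The IgE and IgG4 model forces one variance at Visits 2, 6 and 8 and equal adjacent correlations, so Visit 6 or Visit 8 intervals can be miscalibrated, in a direction the documents do not settle

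*SAP*

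**What the plan says.** Protocol 8.2.5.1 and SAP 3.2.5.1 (Tertiary Efficacy/Immunologic Analyses) use the same model for IgE and IgG4: a constrained longitudinal data analysis (cLDA) with the baseline value in the response vector. On covariance: "A Toeplitz covariance matrix will be used to model the correlation among repeated measurements". The example code in SAP Appendix A confirms the homogeneous form: "REPEATED time / SUBJECT=subj TYPE=TOEP". It has no EMPIRICAL option.

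The means are left free: "Time is treated as a categorical variable so that no restriction is imposed on the trajectory of the means over time". The variances are not, and no reason is given.

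The endpoints are raw changes in level, for example "Change from baseline in IgE level against *Ambrosia artemisiifolia* at Visit 6 and at Visit 8". Neither document states a transformation. Appendix A adds that "The cLDA model assumes that baseline and post-baseline values have a joint multivariate normal distribution".

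The trial flow chart (protocol 6.0) schedules the immunologic sample at Visits 2, 6 and 8, at selected sites only. On the baseline sample it says "The Visit 2 sample should be collected prior to administration of the first dose of study drug".

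If the Toeplitz model does not converge, Appendix A offers only AR(1) estimates as starting values. The plan does mention an unstructured covariance as an option, but only for the daily TCS sensitivity model.

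**The concern.** With three visits, TYPE=TOEP has three parameters: one variance, one lag-1 covariance and one lag-2 covariance. That makes two restrictions on the data:

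- the variance is the same before treatment, before the season and after the season;
- the Visit 2–6 and Visit 6–8 correlations are equal.

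Neither restriction is needed to fit the model, and either may fail. If spread changes over time, the model-based standard error at one of the two post-baseline visits is wrong. The weight given to the baseline value is then wrong too, which costs precision. Confidence intervals and nominal p-values for the immunologic objective would be miscalibrated, with nothing in the plan to detect or absorb it.

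The schedule does not guarantee equal gaps either. Pre-seasonal and co-seasonal treatment last "approximately 12 weeks (up to approximately 20 weeks) of pre-seasonal treatment and approximately 8 weeks of co-seasonal treatment". Visit 6 falls about 2 weeks before the season and Visit 8 about 1 week after it. Visit 2 to Visit 6 is therefore about 12 − 2 = 10 to 20 − 2 = 18 weeks. Visit 6 to Visit 8 is about 2 + 8 + 1 = 11 weeks. The gaps are close at the short end and clearly unequal at the long end.

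**Working it through.** The plan states no sample size, SD, correlation or power for IgE or IgG4, so there is no figure to reproduce. The check asks what the Toeplitz restriction does under stated assumptions.

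**Inputs from the documents.** Three visits; 1:1 allocation; two-sided nominal 5% level; homogeneous Toeplitz; model-based standard errors.

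**Assumed inputs.** SDs at Visits 2:6:8, and correlations written as r(2,6)/r(6,8)/r(2,8). Data are complete.

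**Method.** Let S be the true 3×3 covariance. In large samples the fitted matrix is the Toeplitz W that minimises log|W| + tr(W⁻¹S). With complete data, the cLDA treatment difference at visit t is the difference in means at t minus b times the baseline difference, with b = W₀ₜ/W₀₀. Per subject:

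- model variance = Wₜₜ − W₀ₜ²/W₀₀
- true variance = Sₜₜ − 2b·S₀ₜ + b²·S₀₀
- true size = 2·[1 − Φ(1.96 × √(model variance / true variance))]

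The ratio does not depend on the number of subjects.

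**Worked case, rising SDs 1:1.5:2, correlations 0.8/0.8/0.7, Visit 8.** The fitted common variance is 2.46 and the lag-2 correlation, which equals b, is 0.572.

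- Model variance: 2.46 × (1 − 0.572²) = 1.66
- True variance: 4 − 2 × 0.572 × 1.4 + 0.572² = 2.73
- SE ratio: √(1.66/2.73) = 0.78, so size is 12.7% and coverage 87.3%
- With the correct baseline weight the variance would be 4 − 1.4² = 2.04, so the wrong weight inflates it by 2.73/2.04 − 1 = 34%

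**Other SD patterns, correlations 0.8/0.8/0.7:**

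| SDs at V2:V6:V8 | Size at Visit 6 | Size at Visit 8 |
|---|---|---|
| 1:1.1:1.25 | 4.5% | 7.8% |
| 1:1.25:1.5 | 4.9% | 9.8% |
| 1:1.5:2 | 4.8% | 12.7% |
| 1:0.9:0.8 | 4.9% | 2.7% |
| 1:1.5:1.2 | 10.9% | 4.8% |

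For the rising and falling patterns, the Visit 8 figures are nearly the same at 0.6/0.6/0.5 and 0.9/0.9/0.85. For 1:1.5:1.2, Visit 6 size runs from 6.9% (0.9/0.7/0.65) to 13.6% (0.6/0.8/0.5), while Visit 8 stays at 4% to 5%. The precision loss at Visit 8 under 1:1.5:2 depends strongly on the correlations: 12% at 0.6/0.6/0.5, 34% at 0.8/0.8/0.7 and 91% at 0.9/0.9/0.85.

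**Unequal adjacent correlations with equal SDs.** The fitted lag-1 correlation is the average of the two, and lag 2 is fitted exactly. At 0.6/0.8/0.5 the average is 0.7. At Visit 6 the model variance is 1 − 0.7² = 0.51 and the true variance is 1 − 2 × 0.7 × 0.6 + 0.7² = 0.65. The ratio is 0.886 and the size 8.3%. At 0.9/0.7/0.65 the size is 0.9%, and at the widest gap tried (0.6/0.9/0.5) it is 11.1%. Visit 8 stays at exactly 5.0% in every case.

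**Simulation check (1,500 runs, 100 per arm assumed), size at Visit 8:**

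| Setting | Toeplitz | Unstructured |
|---|---|---|
| Normal, SDs 1:1.5:2 | 13.6% | 6.0% |
| Raw lognormal, means 1:1.5:2 | 14.4% | 6.1% |
| Raw lognormal, constant means | 4.3% | 4.7% |

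Monte Carlo standard error is about 0.6 points at 5% and 0.9 points at 14%.

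**The case against.** The strongest reply is that everything numerical here rests on assumed variances. That is correct. A reader might infer that the Visit 8 intervals are probably too narrow, because antibody levels tend to be skewed and to rise. The documents give no SD, skewness or direction of change for either antibody, and the same method gives intervals that are too wide when SDs fall. The possibility of miscalibration stands; its sign does not.

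A reader might also blame unequal visit spacing for errors at Visit 8. That fails: the Visit 2–8 covariance is a free parameter, and with equal SDs Visit 8 is unaffected. Spacing matters only for Visit 6, which is itself a named endpoint.

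Nor is skewness the problem in itself. Raw lognormal data with constant means held their size; the harm comes when spread grows with the mean. That analysis will be on the raw scale is also an inference from silence.

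Test size is defined with no treatment effect, so only variance growth shared by both arms counts towards it. Growth in the active arm alone bears on interval coverage instead. With SDs 1:1:1.2 on placebo and 1:2:3 on active, Visit 8 coverage is about 86%.

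The code in Appendix A is labelled an example. Its model line is "MODEL y=time tt11 tt12 tt13 tt14 tt21 tt22 tt23 tt24 stratum": four post-baseline times, terms for a second active treatment and a single stratum term. The text describes two post-baseline visits, two arms, and asthma status, age group, season and region nested in season as covariates. The second indicator array is used without a visible declaration, although a line may have been lost in text extraction. This mismatch is mostly clerical.

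Finally, the pulmonary function cLDA refers back to this model. A reader might extend the figures to it, but it uses other visits and was not calculated, so nothing is claimed for it here.

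**Conclusion.** The point holds in a limited form. The plan fixes a covariance structure with two unneeded restrictions, gives no alternative structure or robust standard error, and does not state the analysis scale while assuming joint normality. Under the SD patterns tried, a nominal 5% test at Visit 8 runs from about 3% (falling SDs) to about 13% (rising to 1:1.5:2). If spread peaks at Visit 6, the error is there instead, about 7% to 14%. With equal SDs and adjacent correlations of 0.9/0.7 or 0.6/0.8, Visit 6 size is about 1% or 8%. All of these figures assume complete data and SDs and correlations that are not in the documents, so they show sensitivity and do not predict the result.

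The consequence is small. SAP 3.2.5 treats p-values for tertiary analyses as nominal, and these endpoints lie outside the fixed sequence in SAP 3.2.7. A reader might infer a threat to confirmatory error control; there is none, and the primary and key secondary conclusions do not depend on this model.

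**What to change.** In the SAP, before database lock:

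1. Use TYPE=UN over Visits 2, 6 and 8 for the IgE and IgG4 cLDA. Keep Toeplitz only as a convergence fallback, with empirical standard errors.
2. State the analysis scale in advance. A log scale is recommended if spread grows with the mean; treatment effects are then reported as ratios of geometric means.
3. Rewrite the Appendix A equations and code for three visits, two arms and the covariates listed in the text.

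The cost is a few sentences and lines of code, and three more covariance parameters. The documents do not give the size of the immunologic subset, so convergence cannot be guaranteed, which is why the fallback is needed. No new data are required. SAP 3.2 already allows non-confirmatory changes to be documented in the supplemental SAP before final database lock, so this change needs no protocol amendment.
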